#### 5. Operation of the stroke registers

In the North Karelia County stroke patients are treated either at health centre hospitals or at the North Karelia Central Hospital. In Kuopio County the health centre hospitals, two district hospitals in Varkaus and Iisalmi and the University Central Hospital are in charge of the stroke cases. In Turku most cases of stroke are treated at Turku University Central Hospital and to a lesser extent at the Turku City Hospital. Loimaa District Hospital is responsible for the vast majority of stroke cases in that monitoring area.

A liaison nurse is appointed for the health centre hospitals of each of the monitoring areas. The liaison nurses are in charge of the initial registration of stroke cases admitted to the hospital. The first part of the record form (initial information) will be completed by the hospital first admitting the patients. Four-week follow-up information or information on fatal outcome is given by the hospital where the patient is sited during the follow-up or his/her death. After the record form has been completed by the hospital or the health centre it is sent to the monitoring centre of the area.

Most cases of stroke are treated at the central hospitals, city or district hospitals of the area. In Joensuu, Turku, Loimaa and Kuopio - the locations of the monitoring centres - the register nurse is regularly visiting the out-patient departments of the hospitals checking the admission diagnoses. Cases of definite or possible stroke, even cases of susceptible symptoms are registered. The first part of the record form is completed and the patients are followed-up until discharge, their death or until 28 days has passed. At this stage, the record forms are completed for follow-up information. The register nurses are also regularly checking the discharge diagnoses of the hospitals observing ICD-codes 430 -438 to explore the until then unidentified cases. They are also checking monthly all the death certificates of their monitoring area, extracting the available information and completing the record forms if needed.

All completed record forms are sent without any delay to the register doctor of the monitoring area. A copy of patients' medical record and a copy of the autopsy record will be enclosed with the record forms. At the monitoring centre, the register doctor completes items 25 and 26. Finally, the completed records are sent to the national monitoring centre in the National Public Health Institute.

IV MEDICAL CARE ASSESSMENT FOR ACUTE MYOCARDIAL INFARCTION

## 1. Introduction

Changes in cardiovascular mortality rates might be related to:

- a change in disease incidence, or
- a change in case fatality, or
- both.

A change in case-fatality could be related to changes either in medical care in the affected population or in the natural history of the disease, or in both.

MONICA study is especially concerned in medical care for the acute myocardial infarction. The second main null hypothesis of the MONICA study is, as stated in the Protocol (May 1983 version):

"for the participating centres there is no relationship between

- 10 year trends in case fatality rate (percentage of attacks that are fatal within 28 days)

AND

- 10-year trends in medical care in the attack."

The hypothesis is that the outcome (case fatality,  $O$ ) is related to certain biological and demographical factors (confounding factors,  $C$ ) and medical treatment during the attack ( $T$ )

$O=f(C_i, T_j)$ , where

$O$	outcome
$C_i$	confounding factors
$T_j$	treatment factors

The purpose of the FINMONICA medical care assessment study is

1. to describe the changes in medical care found within the 6-year period 1986-1991; and
2. to study the association of the case fatality with medical care indicators of acute myocardial infarction treatment.

## 2. The general study design

Medical care in the acute myocardial infarction and the subsequent rehabilitation and follow-up consist of the essential part secondary and tertiary prevention in cardiovascular diseases. This medical care comprises of (fig 1.)

- medication prior to the attack
- treatment before hospitalization
- treatment and diagnostic procedures during hospitalization
- treatment and diagnostic procedures during the follow-up period.

[figure not shown]

Figure 6. The sequence of diagnostic and therapeutic procedures

The medical care after the acute myocardial infarction is recorded twice in each case: first during the hospitalization and second during the follow-up since one year has passed from the acute attack.

The hospital care data recorded include the measures prior to the event, the the acute care at the hospital and the diagnostic and therapeutic procedures immediately after the discharge. The long-term medical intervention is assessed according to the follow-up information.

Medical care will be monitored two times during the 6 year period : 1986 and 1991.

[figure not shown]

Figure 7. The time-table of the monitoring of AMI medical care.

### 3. The study material

#### 3.1 Background information

The four FINMONICA acute myocardial infarction registers (South-West Finland consists of two separate AMI registers, Turku and Loimaa) record all suspected AMI cases in their monitoring area. These can be classified as

- sudden deaths (people found dead and resuscitation being unsuccessful),
- deceased during the first 28 days, and
- cases alive after the first 28 days since the attack.

All cases are further classified as definite and possible AMIs, primary ischaemic cardiac arrests and attacks having no AMI. The final diagnosis will be given when all the data concerning the event have been collected.

The total number of registered events in FINMONICA was about 2300 in 1983 (table 11).

Table 11. The number of events in the AMI registers during 1983.

Monitoring area	Both sexes	Men	Women
Kuopio	1000	730	270
North Karelia	800	590	210
Turku	420	320	100
Loimaa	110	80	30
All	2330	1720	610

### 3.2. The sample size, theoretical considerations

#### 3.2.1 Descriptive analysis

The sample size needed to find a difference between two periods (or types of care) in the utilization rates of pharmaceuticals or procedures is:

$$\beta = 1 - \Phi \left( \Phi^{-1} \left( 1 - \frac{\alpha}{2} - \frac{d}{\sqrt{\sigma^2}} \right) + \Phi \left( \Phi^{-1} \left( 1 - \frac{\alpha}{2} \right) - \frac{d}{\sqrt{\sigma^2}} \right) \right)$$

$$\text{where } \sigma^2 = \frac{a(1-a)}{N_1} + \frac{b(1-b)}{N_2}$$

Let  $N_1 = N_2 = N/2 \geq 25$  and  $d \geq 0.05$ , then the last term is very small ( $\leq 0.025$ ) and we can ignore it.

If we assume a significance level  $= 0.05$ , power  $= 0.80$ , then the relationship of  $N_1 = N_2 = N/2$  to  $a$  and  $d$  is as described in table 12.

Table 12.  $N_1 = N_2 = N/2$  and its relationship to  $a$  and  $d$  ( $d=b-a$ ).

$d=$	0.10	0.15	0.20	0.30
$a=$				
0.10	196	98	59	29
0.20	290	137	79	36
0.30	353	160	90	42
0.40	358	171	94	39

The MONICA - protocol (May 1983) suggests a sample size of 500 ( $N/2=250$ ). This enables us to detect all relevant differences, when  $d \geq 0.15$ ,  $\alpha=0.05$  and  $\beta=0.80$ , between two populations, in the first study period. It also enables us to detect differences between two periods of time (e.g. the first and second study period), when  $d \geq 0.10$ .

### 3.2.2 Analysis of associations between different treatment modalities and case fatality

Under preparation.

### 3.3. The study material in 1986 study

The medical care during the acute myocardial infarction event will be assessed in all those cases recorded in some of the FINMONICA myocardial infarction registers and have had at least one medical intervention or an attempt of such. Patients with both a successful or an unsuccessful resuscitation and those without cardiac arrest are included. Those patients who are found dead and therefore have had not any medical interventions, are excluded.

The study cases can be definite, possible, or no AMI in their final diagnostic classification. The one year follow-up questionnaire is mailed only to the cases having definite or possible AMI. The information needed can also be recorded during the follow-up visit.

Only male patients will be included in the assessment study. The registration will take place during six months in 1986.

Table 13 shows how the study material is built up.

Table 13. Estimated number of men in the study material (definite and possible cases) according to the status of the patient and the site of admission

Men	University Hospitals		North Karelia Central Hospitals	District hospitals	Primary health care centres	Total
	Kuopio	Turku				
Unsuccessful resuscitation	10	10	10	15	35	80
Death during the first 28 days	10	10	10	5	5	40
Alive at 28 days	100	80	100	50	80	410
Total	120	100	120	70	120	530

1) Two third of cases are definite by their diagnostic classification

#### 4. The parameters

##### 4.1. The outcome parameters

- The proportion of cases with any medical intervention during the acute MI
- 28-days case fatality
- one year case fatality

##### 4.2. The determinants

Parameters recorded during the hospitalization:

- treatment prior to the current attack
- delay in starting medical interventions
- cardiac arrest and cardiopulmonary resuscitation outside the hospital
- the total length of stay at the hospital
- the length of time with ECG monitoring
- the intensity of medication at hospital
- the treatment procedures at hospital

- the intensity of diagnostics procedures at hospital
- systematic rehabilitation at hospital
- background and miscellaneous data

Parameters recorded at the time of discharge:

- the prescribed drugs
- planned systematic follow-up and rehabilitation

Parameters recorded at the one year follow-up:

- the number of physician visits
- the attendance to a systematic rehabilitation
- medication and therapeutic procedures performed
- diagnostic procedures performed

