### 5.2. Data collection, forms

Form 2	Medical care, in-hospital
Form 3A	Medical care, 12 month follow-up, filled in by the nurse
Form 3B	Medical care, 12 month follow-up, mailed to the patient

These forms are under preparation

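### Survival-dependent care measures are listed as determinants of case fatality without being tied to an outcome they precede or to a risk set

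*Protocol*

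**What the plan says.** All references are to the protocol, Part IV (medical care assessment), unless stated.

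- Section 1 gives as the second purpose "to study the association of the case fatality with medical care indicators of acute myocardial infarction treatment". The model is O = f(C, T): outcome as a function of confounding and treatment factors. It has no time element.
- Section 4.1 names among the outcomes "28-days case fatality" and "one year case fatality".
- Section 4.2, headed as the determinants, puts into one list "the total length of stay at the hospital", "the length of time with ECG monitoring", in-hospital rehabilitation, drugs prescribed at discharge and, from the one-year follow-up, "the number of physician visits". The items are grouped by when they are recorded.
- Section 3.3 keeps men with unsuccessful resuscitation in the material and excludes those found dead. Table 13 expects 80 unsuccessful resuscitations, 40 other deaths by day 28 and 410 men alive at day 28.
- Section 3.2.2, on associations between treatment and fatality, is still to be written. Of the data forms, section 5.2 says: "These forms are under preparation".

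**The concern.** Several listed determinants are partly consequences of the outcome. A man who dies on day 2 has at most two days of stay and monitoring, no rehabilitation that would have begun later, and no discharge prescription. His low exposure follows from his death. This is immortal-time bias with reverse causation, and adjusting for the factors C does not remove it.

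The chosen population makes it worse. Two thirds of the expected deaths by day 28 are unsuccessful resuscitations, with almost no time in which to accrue care.

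At stake is the second purpose of the assessment. If the list is carried as it stands into O = f(C, T), care that does nothing can appear strongly linked to lower fatality.

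**Working it through.** **1. The plan's own figures (Table 13).** 80 + 40 + 410 = 530, as printed. Deaths by day 28: 80 + 40 = 120, and 120/530 = 22.6%. Unsuccessful resuscitations make up 80/120 = 67% of them. Without them, fatality is 40/450 = 8.9%. The protocol gives no effect size or power for the fatality association, so there is no such figure to reproduce.

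**2. Rehabilitation, no true effect.** Assumptions not in the protocol: 60% of men are assigned rehabilitation, it starts on day s, and time to death among those who die is exponential with mean m days.

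- P(rehabilitation | death) = 0.6 × exp(−s/m). With s = 5 and m = 5 this is 0.6 × 0.368 = 0.22.
- Odds ratio = (0.22/0.78)/(0.6/0.4) = 0.19.
- Over s = 3, 5, 7 and m = 3, 5, 8 the range is 0.04 (s = 7, m = 3) to 0.47 (s = 3, m = 8).

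This treats every death as an in-hospital death. If the 80 resuscitation deaths had no chance of rehabilitation, the exposure probability is multiplied by 40/120. Then 0.22/3 = 0.074 and the odds ratio is (0.074/0.926)/1.5 = 0.05, with range 0.01 to 0.11.

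**3. Discharge drugs, no true effect.** Suppose a share p of the 410 survivors receives them and all 120 deaths count as unexposed. Fatality is 0% in the exposed and 120/(530 − 410p) in the unexposed:

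| p | Unexposed fatality |
|---|---|
| 0.25 | 120/427.5 = 28.1% |
| 0.50 | 120/325 = 36.9% |
| 0.75 | 120/222.5 = 53.9% |

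**4. All in-hospital items, simulated with no effect of care.** Table 13 proportions, with resuscitation deaths at time zero. Assumed: planned stay 14 days (SD 4); mean monitoring 3 days; rehabilitation from day 7 offered to half; discharge drugs for half of those discharged alive; mean time to death of the other 40 deaths 2, 4, 7 or 14 days. Stay and monitoring are split at the median. Odds ratios of 28-day death:

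| Item | Protocol's population | Without resuscitation deaths |
|---|---|---|
| Length of stay | 0.00–0.04 | 0.001–0.15 |
| ECG-monitoring time | 0.07–0.14 | 0.23–0.72 |
| Rehabilitation | 0.005–0.10 | 0.02–0.38 |
| Discharge drugs | 0.001–0.05 | 0.003–0.17 |

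**5. Sicker men monitored longer.** If the men who later die in hospital would have been monitored 2 to 5 times longer by plan, the ECG odds ratio is 0.09 to 0.27 in the protocol's population. Without resuscitation deaths it is 0.34 to 2.75, so there the direction can reverse.

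**6. Check of the remedy.** Among admitted men alive at day 7, with only later deaths counted, fatality in exposed and unexposed is 0.3% v 0.3%, 1.7% v 1.7%, 3.4% v 3.4% and 5.1% v 5.1% for the four death-time assumptions. The false benefit disappears.

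**7. One-year items.** No calculation applies. Forms 3A and 3B are completed at 12 months, by a nurse or by post. Part III, AMI register, section 6 sends the one-year letter only to men and women alive at 28 days, and records only the death information for those who die in the year. Exposure is therefore absent for every one-year death.

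**The case against.** The strongest reply is that no analysis has been fixed. Section 3.2.2 is unwritten, and landmarks and risk sets commonly belong to a later analysis plan. Section 1 also defines T as treatment during the attack, which would leave out discharge and one-year items. The list in section 4.2 is ordered by recording time, mixes in background data, and serves the descriptive first purpose too. All of this is correct, and it means that the protocol does not commit itself to a biased analysis. It does not remove the point: length of stay, monitoring and in-hospital rehabilitation fall within the attack even on that definition, and the section labels every item a determinant beside fatality outcomes.

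Stronger readings that a reader might infer are not supported:

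- That only survivors can accrue these items. Stay and monitoring also accrue in men who die, but are cut short. Rehabilitation needs survival only to its start.
- That one-year visits will look protective. Their association with one-year death cannot be estimated.
- That the bias always favours care. For monitoring time it need not, once resuscitation deaths are excluded.
- That the result would test the second main null hypothesis. That hypothesis concerns ten-year trends across participating centres, with a care index that Part I, section 2 leaves undecided.
- That Form 2 lacks start times. It is not shown, and section 4.2 does list delay to the start of interventions. What can be seen is that the existing AMI register form dates onset (item 16) and death (item 32) but records in-hospital rehabilitation only as yes or no (item 19).

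**Conclusion.** The point holds as a badly fixed determinant list. Used directly in O = f(C, T), the in-hospital and discharge items would show benefit from care that has none. The size is large: for rehabilitation an odds ratio of about 0.19 (0.04 to 0.47), and about 0.05 (0.01 to 0.11) with resuscitation deaths counted. These sizes rest on assumed uptake, start days, stay, monitoring and death times. The direction in the protocol's own population was the same throughout the range tried. The consequence is confined to the local second purpose. The items remain sound for describing care, and the in-hospital and discharge items remain sound as exposures for later death among men discharged alive.

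**What to change.** In section 4.2, and in section 3.2.2 when it is written, pair each determinant with an outcome and a risk set:

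- **28-day fatality:** use treatment before the attack, delay, and treatments started within a fixed early window (for example 24 hours), among men alive at its end. Alternatively, use time-dependent exposure.
- **Death after discharge, to one year:** use stay, in-hospital rehabilitation and discharge prescriptions, among men discharged alive, with follow-up counted from discharge. This keeps men discharged early who die before day 28.
- **One-year items:** description only.
- **Form 2:** record start dates and times of treatments, monitoring and rehabilitation.

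The cost is analysis wording and a few fields on a form that is not final. The downside is that deaths inside the early window leave the treatment models and must be reported separately. If all 80 unsuccessful resuscitations die within the window, at most the other 40 expected deaths remain for the 28-day models.

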## 5. Data collection

### 5.1. Data collection, general

Data are collected at two observation points on two separate data forms. The in-hospital data are collected by the register nurses as part of their ordinary work, the event registration. The follow-up data are collected either during patient visits or by mail. The data form therefore has two versions, one to be used at follow-up clinic and the other to be used by mail.

### 5.2. Data collection, forms

Form 2	Medical care, in-hospital
Form 3A	Medical care, 12 month follow-up, filled in by the nurse
Form 3B	Medical care, 12 month follow-up, mailed to the patient

These forms are under preparation

## ANNEXES

**SURVEY QUESTIONNAIRE**  
**INSTRUCTIONS FOR THE RESPONDENT**

Please give answer to the questions by circling the number corresponding the alternative which is best fitting to you or by writing down what is requested in the respective space. Read the question thoroughly before answering.

Example 1. What is your occupation?

Lumberer

Example 2. What is your marital status?

- 1 married or married in common-law
- 2 single
- 3 separated or divorced
- 4 widow

If you are married, circle number 1.

Be careful and give your answer to all questions - even negative answers should be marked either by circling the alternative "no" or by marking "0" in the respective space.

Example 3. Have you had any of the following diseases?

	No	Yes	
Rheumatoid arthritis		1	2
Hypertension	1	2	

Example 4. How many days of vacation did you have last year?

0 days

In some questions there are some alternatives given and them a note: "Proceed to question ..." If the given alternatives do not concern you, you can proceed to this question directly and skip the intervening questions.

**SURVEY****QUESTIONNAIRE**

(as used in the 1982 survey)

1. Sex
  - 1 male
  - 2 female
  
2. Are you
  - 1 married, or married in common-law
  - 2 single
  - 3 separated or divorced
  - 4 widowed
  
3. What is your education?
  - 1 primary, basic or secondary school
  - 2 vocational school
  - 3 high school
  - 4 college or university
  
4. How many years have you had school altogether or studied full-time in your life?  
\_\_\_\_\_ years
  
5. What is your residence on 1.1.1982?
  - 1 present community
  - 2 other community in the present county
  - 3 other county
  
6. Does your household consist, in addition to yourself, of other persons aged 16 or more (husband, wife, children, retired, etc.)?
  - 1 no
  - 2 yes, how many? \_\_\_\_\_
  
7. Do you have children below the age of 16?
  - 1 no
  - 2 yes

8. What is your occupation?

---

9. In which kind of occupation are you involved for most of the year?

- 1 agriculture, farming, forestry
- 2 industrial, mining, construction or other similar occupations
- 3 office work, service occupation or other similar work
- 4 studying
- 5 housewife
- 6 retired
- 7 unemployed

10. In which kind of occupation have you been involved for the longest period in your life?

- 1 agriculture, farming, forestry
- 2 industrial, mining construction or other similar occupations
- 3 office work, service occupation or other similar work
- 4 studying
- 5 housewife
- 6 retired
- 7 unemployed

11. What was the total income of your household last year, taxes not exempted?

- 1 less than 10.000 mk
- 2 10.000 - 20.000
- 3 20.001 - 40.000
- 4 40.001 - 60.000
- 5 60.001 - 80.000
- 6 80.001 - 100.000
- 7 100.001 - 120.000
- 8 120.001 - 140.000
- 9 more than 140.000

**MEDICAL EXAMINATIONS, ILLNESSES**

12. How often did you see a doctor last year? (dentists excluded)

\_\_\_\_\_ times

13. Last year, how often did you go to see a public health nurse or an occupational health nurse or how often did a public health nurse visit you?

\_\_\_\_\_ times

14. Are you retired because of disability?

- 1 no
- 2 yes, partial imbursement
- 3 yes, for a definite period
- 4 yes, indefinitely

15. Have you had acute myocardial infarction confirmed by a doctor? (Check if you are not sure)

- 1 no
- 2 yes    When was the last time:  
          year 19 \_\_\_\_\_  
          Where were you hospitalized?

---

Did you belong to a rehabilitation group after discharge from the hospital?

- 1 no
- 2 yes

16. Have you had stroke, cerebral hemorrhage or cerebral infarction confirmed by a doctor? (Check if you are not sure)

- 1 no
- 2 yes, when was the last time:  
          year 19 \_\_\_\_\_

17. Last year (during the past 12 months), have you had any of the following diseases confirmed or treated by a doctor?

	no	yes
Elevated blood pressure, hypertension	1	2
Heart failure	1	2
Angina pectoris	1	2
Bronchial asthma	1	2
Emphysema, chronic bronchitis	1	2
Gallstones, biliary disease	1	2
Rheumatoid arthritis	1	2
Other musculoskeletal disorders	1	2
Back pain	1	2
Chronic dermatitis	1	2
Chronic pyelonephritis	1	2

18. Do you have diabetes confirmed by a doctor?

- 1 no
- 2 yes, I receive insulin injections
- 3 yes, I receive oral hypoglycemic drugs
- 4 yes, only dietary control

19. How many days, during the last year (12 months), were you in sick leave from your work or did not do your daily work because of illness? (If you do not remember exactly, give an estimation)

\_\_\_\_\_ days

20. How many days, during the last year, were you hospitalized?

\_\_\_\_\_ days

21. During the past week (7 days) have you used any

a) prescription drug

1 no

2 yes

b) non-prescription drug

1 no

2 yes

If you have used any medication during the past week, circle below for which symptom or disease did you use them.

	Pre- scription	Non-pre- scription
Headache	1	2
Joint pain or back-ache	1	2
Other pain	1	2
Common cold, cough or fever	1	2
Restlessness	1	2
Abdominal pain, digestive symptoms or constipation	1	2
Vitamins, stimulants	1	2
Antihypertensive medication	1	2
Cardiac drugs	1	2
Contraceptive pills	1	2
Drugs for skin diseases	1	2
Other medication	1	2

---

---

For which symptom:

22. When did you last have a health check-up i.e. a medical examination not due to symptoms or illness (e.g., when applying for a job or for a driver's license, in the material clinic, or health check-up of the mobile clinic)?
- 1 during the past 6 months
  - 2  $\frac{1}{2}$  - 1 year ago
  - 3 1 - 5 years ago
  - 4 more than 5 years ago
  - 5 never
23. Has your blood cholesterol ever been measured?  
When was the last time?
- 1 during the past 6 months
  - 2  $\frac{1}{2}$  - 1 year ago
  - 3 1 - 5 years ago
  - 4 more than 5 years ago
  - 5 never
  - 6 I don't know
24. Have you ever been told that you have high or elevated blood cholesterol or fat levels?
- 1 no
  - 2 yes
25. Has your blood pressure ever been measured? When was the last time?
- 1 during the past 6 months
  - 2  $\frac{1}{2}$  - 1 year ago
  - 3 1 - 5 years ago
  - 4 more than 5 years ago
  - 5 never
26. How many times has your blood pressure been measured during the past year (12 months)?  
\_\_\_\_\_ times
27. Have you ever been told that you have high or elevated blood pressure?
- 1 no (go to question 32)
  - 2 yes

28. In which age was your elevated blood pressure first discovered?

\_\_\_\_\_ years

29. Have you ever used antihypertensive drugs?

1 no (go to question 32)

2 yes

30. When did you last take antihypertensive drugs?

1 today or yesterday

2 2 - 7 days ago

3 1 week to 1 month ago

4 1 month to  $\frac{1}{2}$  year ago

5  $\frac{1}{2}$  year to 1 year ago

6 1 - 2 years ago

7 2 - 5 years ago

8 more than 5 years ago

31. If you don't use antihypertensive drugs what is the main reason? (Choose the most important)

1 the doctor told me to stop

2 the public health nurse told me to stop

3 the medication caused side-effects for me

4 I don't like to use drugs

5 the prescription wasn't refilled

0 I do take antihypertensive drugs at the moment

32. Has your father had, in the age of 60 years or less, any of the following diseases?

a. myocardial infarction, angina pectoris

1 no

2 yes

b. stroke

1 no

2 yes

33. Has your mother had, in the age of 60 years or less, any of the following diseases?
- a. myocardial infarction, angina pectoris
    - 1 no
    - 2 yes
  - b. stroke
    - 1 no
    - 2 yes

